2.4.5 Analyses of safety data

The summary of safety results will be presented by treatment group. The safety data except hypoglycemia will be summarized for the entire 52-week double-blind treatment period. The hypoglycemia will be summarized for the 18-week randomized core treatment period and the entire 52-week double-blind treatment period (see [Section 2.4.5.1](#)).

The “observation period” defined in [Section 2.1.4](#) is applicable in all safety analyses for the classification of AEs, determination of treatment-emergent Potentially Clinically Significant Abnormality (PCSA) values and the last on-treatment value for the laboratory, vital sign and ECG.

General common rules

All safety analyses will be performed on the safety population as defined in [Section 2.3.2](#), unless otherwise specified, using the following common rules:

- Safety data in patients who do not belong to the safety population (eg, exposed but not randomized) will be listed separately
- The baseline value (with the exception of serum creatinine and eGFR) is defined as the last available value before the first dose of double-blind IMP. For serum creatinine and eGFR, the baseline value is defined as the average of all values before the first dose of double-blind IMP.
- PCSA values are defined as abnormal values considered medically important by the Sponsor according to predefined criteria/thresholds based on literature review and defined by the Sponsor for clinical laboratory tests, vital signs, and ECG [[Appendix A](#)].
- PCSA criteria will determine which patients had at least 1 PCSA during the treatment-emergent adverse event period, taking into account all evaluations performed during the treatment-emergent adverse event period, including nonscheduled or repeated evaluations. The number of all such patients will be the numerator for the treatment emergent PCSA percentage
- The treatment-emergent PCSA denominator by group for a given parameter will be based on the number of patients assessed for that given parameter in the treatment-emergent adverse event period by treatment group on the safety population.
- For laboratory parameters cited in the protocol as efficacy endpoints (including HbA1c and plasma glucose, etc.), PCSA summaries will not be provided. These parameters will be summarized in [Section 2.4.4](#).
- For quantitative safety parameters based on central laboratory/reading measurements, descriptive statistics will be used to summarize results and change from baseline values by visit and treatment group for the entire 52-week double-blind treatment period only. Summaries will include the last on-treatment value. The last on-treatment value is commonly defined as the value collected at the same day/time of the last administration of

IMP. If this value is missing, this last on-treatment value will be the closest value prior to the last dose administration of IMP during the entire 52-week treatment period.

- The analysis of the safety variables will be essentially descriptive and no systematic testing is planned. Relative risks versus placebo and their 95% confidence intervals may be provided, if relevant
- Selected safety analyses will be summarized by age, gender, racial subgroups, and any pertinent subgroups (see details in [Section 2.4.5.1](#) and [Section 2.4.5.2](#)).

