--	--

	amount of treatment administered. Patients will be analyzed for safety analyses according to the treatment actually received. The safety analyses will be provided for the 18-week randomized Treatment Period and for the entire 52-week double-blind Treatment Period.
DURATION OF STUDY PERIOD (per patient)	Up to 60 weeks, including an up to 6-week Screening Period (comprised of an up to 2-week Screening phase and a 4-week, Lantus titration/single-blind placebo Run-in Phase), a 52-week double-blind Treatment Period, and a 2-week post-treatment Follow-up Visit.
STUDY COMMITTEES	Steering committee:  Yes  No Data monitoring committee:  Yes  No Adjudication committee:  Yes  No

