4.4 RATIONALE FOR STUDY DESIGN AND CONTROL GROUPS

This study is designed to assess the efficacy and safety of sotagliflozin (compared to placebo) when used as add-on therapy to basal insulin (Lantus), alone or in combination with oral antidiabetes drugs (OADs). Patients will be switched from their current basal insulin to Lantus (1:1 dose conversion, or 20% reduction if on treatment with Toujeo or Neutral Protamine Hagedorn [NPH] twice daily) and will have a 4-week dose titration period to improve their basal insulin dose prior to Randomization, utilizing a standard titration algorithm. During this period, compliance with the algorithm will be reviewed by an internal group blinded to the treatment assignment and investigators will be contacted as needed to encourage adherence to titration algorithm. During this Lantus titration period, the dose of concomitant OADs should stay unchanged, except if decreases are needed due to hypoglycemia.

The primary endpoint is HbA1c reduction from Baseline to Week 18 because it is expected that sotagliflozin can provide significant additional glycemic efficacy even in an advanced T2D population with presumed beta cell failure. During the first 18 weeks no adjustment of Lantus is permitted (except for safety reasons or if rescue criteria are met) to enable the assessment of the effect of randomized treatment drug on top of a stable background therapy of insulin \pm OADs. After Week 18, titration of Lantus may resume following the same titration algorithm utilized during the Run-in period. This will enable the assessment of the effect of the randomized study drug in a context of total dose of insulin being simultaneously adjusted and more typical of a real-world setting. Prandial insulin or GLP-1 agonists will be the recommended rescue therapy for patients on a stable regimen of oral antihyperglycemic agents who cannot adequately achieve glycemic control by up-titrating their Lantus dose, as per international diabetes treatment guidelines (13, 14). However, the investigator will be allowed to choose from any antidiabetic agent (with the exception of the SGLT2 inhibitors class) according to their clinical judgment and in line with the local standard of care. The protocol stipulates that patients be provided rescue therapy according to increasingly stringent hyperglycemia criteria (based on FPG and/or HbA1c) as aligned with regulatory guidance (15).

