11.4.3 Analyses of safety data

The summary of safety results will be presented by treatment group. All safety summaries will be descriptive; no statistical significance tests will be performed on safety data.

Safety endpoints are presented in [Section 9.2](#). These analyses will be based on the safety population as defined in [Section 11.3.3](#). Patients will be analyzed for safety analyses according to the treatment actually received. The safety analyses will be provided for the 18-week randomized core Treatment Period and for the entire 52-week double-blind Treatment Period, unless specified otherwise.

The following definitions will be applied to laboratory parameters and vital signs:

- The potentially clinically significant abnormality (PCSA) values for clinical laboratory tests and vital signs are defined as abnormal values considered medically important by the Sponsor's Global Pharmacovigilance and Epidemiology department and in effect at the time of the final SAP approval. The PCSA criteria for parameters not cited in the protocol as safety parameters will not be analyzed.
- The PCSA criteria will determine which patients had at least 1 PCSA during the on-treatment period, taking into account all evaluations performed during the on-treatment period, including unscheduled or repeated evaluations. The number of all such patients will be the numerator for the on-treatment PCSA percentage.

The "observation periods" defined in [Section 9.2](#) are applicable for classification of AEs, determination of on-treatment PCSA values and the last on-treatment value for the laboratory, vital sign and ECG parameters.

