2.4.5.1 Analyses of hypoglycemia

Analyses of hypoglycemia will be performed on the TEAE period as defined in [Section 2.1.4](#). For the purpose of hypoglycemia analyses during the 18-week randomized core treatment period, the TEAE period for 18-week randomized core treatment period is (1) the time from the first administration of the double-blind IMP up to 1 day after the last administration of IMP if the patient discontinued treatment on or before Visit 12 (or Day 126 if Visit 18 date is missing), or (2) the time from the first administration of the double-blind IMP to the administration at Visit 12/Week 18 (or Day 126 if Visit 12/Week 18 date is missing) if the patient remained treated beyond Visit 12/Week 18. Hypoglycemia will be classified as severe hypoglycemia, documented symptomatic hypoglycemia, asymptomatic hypoglycemia, probable symptomatic hypoglycemia or relative hypoglycemia (see [Section 2.1.4.1](#)).

The number (%) of patients with any hypoglycemia, severe hypoglycemia and documented symptomatic hypoglycemia will be summarized respectively by treatment group during the TEAE period, as well as the incidence rate in patient years. Two types of incidence rates will be presented: the number of patients with at least 1 event per 100 patient-years (calculated as the number of patients with at least 1 event / total exposure in 100 patient-years), and the number of events per 100 patient-years (calculated as the total number of events / total exposure in 100 patient-years). Note: here exposure (in days) is the duration of TEAE period, ie, duration of IMP treatment in days +1 (see [Section 2.1.4](#)).

The summary of frequency and incidence rate in patient years for severe hypoglycemia or documented symptomatic hypoglycemia will be provided as appropriate by gender (Male, Female), age group (<50, ≥50 to <65, ≥65 years), race (White, Black or African American, Asian, Other), sulfonylurea use at Week -1 (yes, no).

The number (%) of patients with at least 1 severe hypoglycemia or documented symptomatic hypoglycemia during the TEAE period, as well as the corresponding number of events, will be summarized as necessary by hour of the day for each treatment group, using the following hour intervals: ≥23:00 to <06:00, ≥06:00 to <10:00, ≥10:00 to <14:00, ≥14:00 to <18:00, ≥18:00 to <23:00.

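### The SAP plans 18-week safety incidence tables for hypoglycemia only, although the protocol plans safety analyses for both the 18-week and the 52-week period

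*SAP*

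**What the plan says.** The protocol synopsis, under Analysis of Safety Data, plans both periods without qualification: "The safety analyses will be provided for the 18-week randomized Treatment Period and for the entire 52-week double-blind Treatment Period". Protocol 11.4.3 makes both periods the default and leaves room for exceptions: "The safety analyses will be provided for the 18-week randomized core Treatment Period and for the entire 52-week double-blind Treatment Period, unless specified otherwise".

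SAP 2.4.5 reverses the default. For everything but hypoglycemia: "The safety data except hypoglycemia will be summarized for the entire 52-week double-blind treatment period". For hypoglycemia: "The hypoglycemia will be summarized for the 18-week randomized core treatment period and the entire 52-week double-blind treatment period". For quantitative central-laboratory parameters the same section is explicit, planning summaries "by visit and treatment group for the entire 52-week double-blind treatment period only". SAP 2.4.5.1 defines an 18-week treatment-emergent window, but limits its use: "For the purpose of hypoglycemia analyses during the 18-week randomized core treatment period". In the safety part of SAP Appendix C, only the hypoglycemia row names the 18-week period.

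The visible rows of the change tables in SAP 1.5 and 1.6 do not mention this narrowing. Several rows of Table 2 in SAP 1.6 are blacked out, so a reason may exist there.

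**The concern.** Week 18 is the time of the primary endpoint. Protocol 4.4 explains that Lantus is held until then "to enable the assessment of the effect of randomized treatment drug on top of a stable background therapy of insulin". From Week 19 Lantus is titrated to target. A reader of the study report would want the adverse event profile by arm over the same 18 weeks as the main efficacy result, and the protocol planned to give it.

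Under the SAP, adverse event tables give the crude percentage of patients with at least one event, each patient counted once per event. A difference that appears early and then fades would be shown only after 34 further weeks of first events have been added to both arms. Events with a plausible early onset on the listed events of special interest, such as diarrhea, volume depletion and genital mycotic infection, are where this would matter.

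**Working it through.** No stated figure needs reproducing; the core of the check is a comparison of texts.

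**1. Which outputs cover Weeks 0 to 18 by themselves?**

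| Output | Protocol | SAP |
|---|---|---|
| Hypoglycemia incidence | 18 and 52 weeks | 18 and 52 weeks (2.4.5, 2.4.5.1) |
| TEAEs, serious TEAEs, TEAEs leading to discontinuation | 18 and 52 weeks by default | 52 weeks (2.4.5) |
| Events of special interest | 18 and 52 weeks by default | 52 weeks (2.4.5) |
| PCSA | 18 and 52 weeks by default | any time in the TEAE period (2.4.5.4, 2.4.5.5) |

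**2. Does another SAP output fill the gap?** Four come near it:
- 18-week IMP discontinuations with reasons (SAP 2.2) and Kaplan-Meier plots of discontinuation due to AEs (SAP 2.2) concern stopping treatment, not the incidence of events.
- Laboratory and vital-sign summaries at scheduled visits (SAP 2.5.4) include visits up to Week 18, but describe measurements, not events.
- Adverse event listings carry onset date and study day (SAP 2.4.5.2), so counts could be rebuilt by hand, but a listing does not compare arms.
- Patient-year rates, and Kaplan-Meier curves of time to a safety event, are specified for hypoglycemia only (SAP 2.4.5.1).

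**3. How different is the background in the two periods?**
- Routine Lantus titration is open in 34/52 = 65% of the 52-week period and in none of the 18-week period (Protocol 8.2.1.3; changes for safety or rescue remain possible).
- Antihypertensives are held for 12 weeks (Protocol 6.1.2, 8.8.1). They may change in 40/52 = 77% of the 52-week period and also in 6/18 = 33% of the 18-week period.
- Rescue criteria apply from Day 1 (Protocol 8.2.4), so rescue is possible throughout both periods.

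Only routine Lantus titration separates the two periods cleanly.

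**4. How much could a 52-week crude table dilute an early difference?** The documents give no event rates, so this is an illustration. Assume a placebo 18-week incidence p of 5% or 10%, a constant placebo hazard h = −ln(1 − p)/18 per week, a hazard ratio of 2 in Weeks 0 to 18 and r afterwards, and complete follow-up.

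Week 18: placebo p; sotagliflozin 1 − exp(−2 × 18h).
Week 52: placebo 1 − exp(−52h); sotagliflozin 1 − exp(−h(2 × 18 + 34r)).

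| p | Period | r | Sotagliflozin | Placebo | Ratio | Difference (points) |
|---|---|---|---|---|---|---|
| 5% | 18 weeks | – | 9.75% | 5.0% | 1.95 | 4.75 |
| 5% | 52 weeks | 2 | 25.6% | 13.8% | 1.86 | 11.9 |
| 5% | 52 weeks | 1.5 | 22.0% | 13.8% | 1.59 | 8.2 |
| 5% | 52 weeks | 1 | 18.1% | 13.8% | 1.31 | 4.3 |
| 10% | 18 weeks | – | 19.0% | 10.0% | 1.90 | 9.0 |
| 10% | 52 weeks | 2 | 45.6% | 26.2% | 1.74 | 19.4 |
| 10% | 52 weeks | 1.5 | 39.9% | 26.2% | 1.52 | 13.7 |
| 10% | 52 weeks | 1 | 33.6% | 26.2% | 1.28 | 7.4 |

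The ratio falls clearly only when the hazard ratio itself falls after Week 18. Even at r = 1 the absolute difference shrinks only modestly (4.75 to 4.3 points, 9.0 to 7.4 points). If the hazard ratio stays at 2, the 52-week table shows the larger absolute difference.

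**The case against.** The strongest reply is that the SAP was entitled to do this. Protocol 11.4.3 foresees exceptions, and SAP 2.4.5 states one clearly and consistently with Appendix C. The safety objective (Protocol 5.2) covers the whole 52 weeks, and Protocol 9.2 defines the TEAE period regardless of rescue. The Protocol 4.4 rationale for fixed Lantus concerns the HbA1c endpoint. The outcome tied most directly to insulin, hypoglycemia, keeps its 18-week analysis. Safety is descriptive, so no error rate changes, and the 52-week tables contain every 18-week event.

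Most of this stands. It rules out calling the SAP in breach, and the redacted rows rule out calling the change undocumented. It does not answer the unqualified synopsis statement, nor does it supply a comparison of adverse event incidence by arm over 18 weeks.

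A reader might also infer that the 52-week tables are confounded by rescue and antihypertensive changes while 18-week tables would not be. The documents do not support that. The synopsis allows prandial insulin or GLP-1 agonist rescue within the first 18 weeks, and antihypertensives may change in Weeks 12 to 18. Nor has the SAP dropped all early safety information: the outputs in step 2 of the working remain.

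**Conclusion.** The discrepancy is real but modest. The protocol plans safety analyses for 18 and 52 weeks. The SAP keeps 18-week incidence summaries for hypoglycemia only, gives no visible reason, and plans no other output that compares AE or EOSI incidence by arm over the primary-endpoint period.

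The 18-week period is a cleaner background for routine Lantus titration only. The possible loss is confined to early-onset effects that fade: on the assumed rates, a risk ratio of about 1.9 at Week 18 reads as about 1.3 at 52 weeks if the hazard ratio falls to 1, and is not materially diluted if it stays constant. These figures rest on assumed incidences and hazard ratios and say nothing about what this trial will show. No test, error rate or sample size is affected.

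**What to change.** In SAP 2.4.5 and Appendix C, add 18-week versions of these tables: TEAE overview, serious TEAEs, TEAEs leading to discontinuation, TEAEs by SOC and PT, and events of special interest. An 18-week PCSA table is optional, because the by-visit summaries already show the early laboratory and vital-sign data.

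Use the SAP 2.4.5.1 window. For patients who stop on or before Visit 12, replace its 1-day tail with the 10-day tail that SAP 2.1.4 sets for events other than hypoglycemia. When reusing that window, correct its reference to a Visit 18: the schedule ends at Visit 16, and Week 18 is Visit 12.

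The cost is a second period filter on existing table programs and more descriptive tables to review. It needs no new data and no protocol amendment, since it restores the protocol's default.

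If the narrowing is intended, state the reason in SAP 1.5 or 1.6 and reconcile it with the protocol synopsis and Section 11.4.3.

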2.1.4 Safety endpoints

The safety analysis will be based on the reported adverse events, hypoglycemia, and other safety information, such as clinical laboratory data, vital signs, electrocardiogram (ECG), and physical examination, etc.

Observation period

The observation period will be divided into 4 epochs:

- The **screening** epoch is defined as the time from the signed informed consent date up to the first administration of the double-blind IMP.
- The **treatment** epoch is defined as the time from the first administration of the double-blind IMP to the last administration of the double-blind IMP.

- The **residual treatment** epoch is defined as the time from the last administration of the double-blind IMP up to 10 days (1 day for hypoglycemia) after the last administration of the double-blind IMP.

The treatment-emergent adverse event (TEAE) period will include both **treatment** and **residual treatment** epochs (see the TEAE period of the 18-week randomized core treatment period for analyses in hypoglycemia in [Section 2.4.5.1](#)).

- The **posttreatment** epoch is defined as the period of time starting the day after the end of the treatment-emergent adverse event period up to the last protocol-planned visit or the resolution/stabilization of all serious adverse events (SAE), adverse events of special interest (AESI) and events of special interest (EOSI), whichever is later.

The on-study observation period is defined as the time from start of double-blind treatment until the end of the study (defined as the last scheduled visit for those who completed the study and the date collected on e-CRF page “Completion of End of Study/Follow-up” for those who did not complete the study).

The post-study observation period is defined as the time from the day after the end of the study until the resolution/stabilization of all SAE, AESI and EOSI if applicable.

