2.1.4.4 Laboratory safety variables

Clinical laboratory data consists of blood analysis, including hematology, clinical chemistry, and urinalysis. Clinical laboratory values will be summarized in both standard international units and conventional units when applicable.

Blood samples for clinical laboratories will be taken at designated visits (see study flowchart in [Appendix D](#)). The following laboratory data will be measured at a central laboratory:

- Hematology

- **Red blood cells and platelets:** hemoglobin, hematocrit, red blood cell, platelets count
- **White blood cells:** white blood cell, neutrophils, lymphocytes, monocytes, basophils, eosinophils
- Clinical chemistry
 - **Metabolism:** glucose (serum), creatine phosphokinase (CPK)
 - **Electrolytes and minerals:** sodium, potassium, chloride, bicarbonate (ie, carbon dioxide), calcium, phosphorus, magnesium
 - **Renal function:** blood urea nitrogen (BUN), creatinine, uric acid
 - **Liver function:** total protein, albumin, ALT, aspartate aminotransferase (AST), alkaline phosphatase (ALP), total bilirubin, Lactic acid dehydrogenase (LDH)
- Lipid parameters (fasting): total cholesterol (TC), high density lipoprotein cholesterol (HDL-C), low density lipoprotein cholesterol (LDL-C) (calculated by Friedwald equation, See [Section 2.5.1](#)), Non-HDL-C (calculated as the difference between TC and HDL-C), triglycerides (TG).
- Pancreatic enzymes: lipase, amylase.
- Beta-hydroxybutyrate (BHB)
- Markers of bone and calcium metabolism
 - 25-hydroxyvitamin D,
 - 1,25-dihydroxyvitamin D,
 - Parathyroid hormone (PTH),

Urine samples will be collected at designated visits (see study flowchart in [Appendix D](#)). The following laboratory data will be measured at a central laboratory:

- Urine dipstick includes: specific gravity, pH, protein, blood, ketones, bilirubin, urobilinogen, nitrite, and leukocyte esterase
- Urine microscopy includes, but is not limited to: detection of formed cellular elements, casts, bacteria, yeast, parasites, and crystals in centrifuged urine sediment

Serum glucose and Calculated UACR will be presented as efficacy parameters in [Section 2.4.4](#). For calculated eGFR, PCSA summaries will be presented in the safety section while descriptive summaries in the efficacy section.

Technical formulas are described in [Section 2.5.1](#).

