2.4.5.4 Analyses of laboratory variables

Laboratory parameters will be grouped and summarized by biological function as described in [Section 2.1.5.2](#).

The summary statistics (including number, mean, median, Q1, Q3, standard deviation, minimum and maximum) of all laboratory variables (central laboratory values and changes from baseline) will be calculated for each visit or study assessment (screening, run-in, baseline, postbaseline time point, last on-treatment value) by treatment group.

The incidence of PCSAs (list provided in [Appendix A](#)) at any time during the treatment-emergent adverse event period will be summarized by biological function and treatment group whatever the baseline level and/or according to the following baseline status categories:

- Normal/missing
- Abnormal according to PCSA criterion or criteria

For parameters for which no PCSA criteria are defined, similar table(s) using the normal range will be provided.

All measurements collected during the TEAE period, including values from unscheduled visits, will be considered for the PCSA summaries. These summaries will include patients in the safety population who have at least 1 assessment performed during the TEAE period. When a PCSA definition involves a change from baseline value, patients must also have a baseline value to be included in the summaries, and when required by the definition of the abnormality, patients must also have available laboratory normal ranges.

A listing of patients with at least 1 post-baseline PCSA (or out of normal range when no PCSA criterion is defined) will be provided which will display the entire patients' profile across time for all parameters belonging to the corresponding biological function. Individual data listings will include the following flags when applicable:

- Baseline values will be flagged "B".
- Normal laboratory ranges, available for most laboratory parameters, will be identified as ULN and LLN. Baseline, last on-treatment value, and individual data will be flagged "L" if the value is below the LLN and will be flagged "H" if it is above the ULN.
- Laboratory PCSA criteria will be used for the corresponding laboratory parameters. Values reaching a PCSA limit will be flagged (+, ++, -, or -- depending upon the direction and level of the abnormality). Flags for WBC and differential counts will be determined using data expressed in international units.

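### SAP 2.1.4.4 and 2.4.5, read together, drop the protocol's by-arm count of abnormal serum glucose without a stated reason, leaving some masked low values uncounted

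*SAP*

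**What the plan says.** **Protocol.** Table 4 in 9.2.1.3 places serum glucose under clinical chemistry in its list of blood safety parameters. Section 11.4.3.5 plans the number and percentage of patients with a PCSA, by arm, for each clinical laboratory test. Section 11.4.3 sets one limit: "The PCSA criteria for parameters not cited in the protocol as safety parameters will not be analyzed". Serum glucose is cited as a safety parameter, so this limit does not remove it.

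**SAP.** Section 2.1.4.4 lists serum glucose among the laboratory safety variables, under Metabolism ("glucose (serum), creatine phosphokinase (CPK"). Later in the same section comes "Serum glucose and Calculated UACR will be presented as efficacy parameters in" Section 2.4.4, followed by the only laboratory exception: "For calculated eGFR, PCSA summaries will be presented in the safety section while descriptive summaries in the efficacy section". The common rules in 2.4.5 add: "For laboratory parameters cited in the protocol as efficacy endpoints (including HbA1c and plasma glucose, etc.), PCSA summaries will not be provided". Section 2.4.5.4 then says that the incidence of Appendix A PCSAs "will be summarized by biological function and treatment group whatever the baseline level", with no carve-out. Appendix A has a low-glucose criterion: at or below 3.9 mmol/L and below the lower limit of normal.

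**Masking and event source.** Protocol 8.3.1 masks central fasting glucose, plasma or serum, from sites and patients after randomization. SAP 2.1.4.1 identifies hypoglycemia from the dedicated e-CRF page.

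**The concern.** All patients take basal insulin, and after Week 18 the dose is again titrated toward a fasting target of 80-100 mg/dL (Protocol 8.2.1.3). Hypoglycemia is a named safety endpoint, and the protocol puts forward a lower hypoglycemia risk as a possible benefit (4.5). The event counts depend on patients testing and sites recording. Central serum glucose is collected in every arm, is masked, and does not depend on either step. The protocol planned to count its abnormal values. If that count goes, an independent descriptive check on asymptomatic low glucose goes with it, and the SAP does not say why.

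**Working it through.** **1. What the protocol plans.** Table 4 cites serum glucose as a safety parameter. Section 11.4.3 removes only parameters not so cited, and 11.4.3.5 covers each clinical laboratory test. Together these plan a serum glucose PCSA count by arm. Fasting plasma glucose (FPG) is different: it is an efficacy endpoint (9.1.2) and is not in Table 4, so the protocol does not itself call for an FPG PCSA count.

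**2. What the SAP does.** No sentence says outright that serum glucose has no PCSA summary. The omission follows from three statements: 2.1.4.4 moves it to efficacy; 2.4.5 withholds PCSA summaries for laboratory efficacy endpoints, with plasma glucose as an example; and the exception names eGFR alone. Systolic and diastolic pressure are efficacy endpoints that keep PCSA counts, but they are vital signs. None of the legible rows in SAP Tables 1 and 2 explains the change; some rows of Table 2 are redacted.

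**3. Where the text leaves room.** The 2.4.5 rule applies to parameters that the protocol cites as efficacy endpoints. The protocol cites FPG, not serum glucose. Section 2.4.5.4 has no exclusion. The efficacy text in 2.4.4 and the efficacy tables in Appendix C never name serum glucose, although 2.1.4.4 sends it there.

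**4. Tracing a low central value.**
- The site does not see it (Protocol 8.3.1). The laboratory alerts described in Protocol 8.2.4 are for values above the rescue thresholds.
- It reaches the e-CRF page, and so the any-hypoglycemia count in SAP 2.4.5.1, only if self-monitoring (SMBG) or symptoms also pick up a low.
- The efficacy summaries for FPG give a minimum by visit and arm, not a number of patients below a limit.
- The continuous glucose monitoring (CGM) sub-study counts low sensor readings in about 132 patients. That leaves 560 - 132 = 428, or 428/560 = 76.4%, outside it. Its post-randomization sensors are worn for 14 days in Weeks 18 and 19.

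**5. Scale.** Clinical chemistry is drawn on treatment at Weeks 4, 8, 12, 18, 26, 39 and 52, which is 7 visits. With full retention:

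| Arm | Scheduled samples |
|---|---|
| 400 mg | 7 x 280 = 1,960 |
| 200 mg | 7 x 140 = 980 |
| Placebo | 7 x 140 = 980 |
| Total | 3,920 |

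Dropout lowers these figures. Unscheduled values raise them, since the PCSA rule works by "taking into account all evaluations performed during the treatment-emergent adverse event period, including nonscheduled or repeated evaluations". The Week 54 sample does not count: it falls 14 ± 3 = 11 to 17 days after the last dose, and the laboratory window runs "up to 10 days (1 day for hypoglycemia) after the last administration of the double-blind IMP".

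**6. What an empty row would show.** The exact two-sided 95% upper limit for zero events is 1 - 0.025^(1/n). For n = 280 it is 1.3%; for n = 140 it is 2.6%. This assumes that every randomized patient has a central value in the window.

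**The case against.** The strongest reply is that the SAP is consistent. The 2.4.5 bullet is one of the common rules for all safety analyses, and 2.4.5.4 sits beneath it. Appendix A is a generic sponsor list that also holds HbA1c above 8%, which the same bullet excludes, so a glucose row there does not show that a table was planned. This largely stands. A reader might infer a flat contradiction between 2.4.5 and 2.4.5.4, and the text does not support that: the common rule plausibly governs. What it leaves open is whether the rule reaches serum glucose, and why a protocol-planned count should go.

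Second, hypoglycemia is already well covered. Asymptomatic episodes are recorded on the e-CRF. Fasting SMBG is mandatory on 3 days a week to Week 18, and on 3 days in the week before each visit afterwards (Protocol Table 3). SMBG therefore samples much the same fasting state around the same visits. This also stands, and it limits the gap to lows seen only by the central laboratory.

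Third, a reader might call every such value a missed asymptomatic hypoglycemia. The documents do not go that far. Protocol 10.6.1 defines that event on plasma glucose and asks investigators to clarify low readings with the patient, which cannot be done with a masked value. Nor does silence about low-glucose alerts prove that the laboratory sends none.

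**Conclusion.** The point holds for serum glucose, as a minor matter worth considering. The protocol plans a by-arm PCSA count, and the most natural joint reading of SAP 2.1.4.4 and 2.4.5 removes it without a stated reason. The step from those sections to omission is partly inference.

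The consequence is confined to asymptomatic lows found only by the central laboratory and, through them, the any-hypoglycemia category. A reader might infer that the hypoglycemia comparison as a whole is unreliable. It is not: severe and documented symptomatic hypoglycemia and every tested endpoint are untouched, and SMBG remains the main safety channel. A reader might also take 3,920 as a count of lost events. It is the sampling schedule under full retention; the number of low values among those samples cannot be estimated from the documents.

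**What to change.** In SAP 2.1.4.4, and in the 2.4.5 bullet, give serum glucose the same exception as eGFR. Then tabulate, by arm, the number and percentage of safety-population patients with at least one central serum glucose meeting the Appendix A low criterion (at or below 3.9 mmol/L and below the lower limit of normal) in the treatment-emergent period. The existing 2.4.5 rules settle the rest: unscheduled values count, and the denominator is the patients assessed for serum glucose in that period. Label the table a laboratory finding and keep it separate from the e-CRF hypoglycemia count.

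The low side matters most, because high values are already followed through the efficacy summaries and the rescue criteria. If the sponsor prefers no table, 2.4.5.4 should exclude serum glucose expressly and SAP 1.6 should record why the protocol plan was changed.

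An FPG row, a row below 3.0 mmol/L (a threshold already in Protocol 10.6.1), same-date matching to e-CRF events and an 18-week version are optional; they go beyond what the protocol planned for this count.

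The cost is one descriptive table from data already collected, and some risk that readers confuse it with the e-CRF count, which the label should prevent.
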